### 9.2.3 Drug Similarity VAS

The Drug Similarity unipolar VAS items provide an estimate of how close the drug classes with which drug users have familiarity with are when compared to the test drug. On a scale ranging from “Not at all similar” to “Very similar,” subjects are asked to compare a drug they had actually received to a comparison drug they previously declared having familiarity/experience with taking.

A Drug History form is completed during the Screening Phase and used to create a subject-specific Drug Similarity measure for use during the Treatment Phase. Drugs that a subject has not personally experienced often enough to use as a standard of comparison (< 2 lifetime uses of a given drug), will not be included in their questionnaire.

**Table 9-6. Description of Drug Similarity Visual Analog Scales**

Description	Question Text	Response Anchors
Drug similarity	How similar is the drug you most recently received to [drug name] ? where the question will be repeated for each [drug name] in the following list:	0: Not at all similar 100: Very similar

 
▪ Phencyclidine (PCP)
 
▪ Caffeine
 
▪ Cocaine (including crack)
 
▪ Codeine, morphine, oxycodone, hydrocodone, hydromorphone
 
▪ Ecstasy (MDMA)
 
▪ Heroin
 
▪ LSD
 
▪ Methadone
 
▪ Nicotine
 
▪ Placebo
 
▪ D-amphetamine (“Speed”) or methamphetamine
 
▪ Pseudoephedrine (Sudafed)
 
▪ Halcion, Xanax, or Valium
 
▪ Ketamine (“Special K”)
 
▪ THC (marijuana, cannabis, hash)
 
		
At the conclusion of the list of specific drugs, a general question will appear:		
Overall Familiarity	How familiar was the effect of the drug you most recently received?	0: Very unfamiliar 100: Very familiar

### 9.2.4 Addiction Research Center Inventory (ARCI)

The Addiction Research Center Inventory (ARCI) Morphine-Benzedrine Group (MBG), Amphetamine (A), Benzedrine Group (BG), Pentobarbital-Chlorpromazine-Alcohol Group (PCAG), and LSD scales will be administered as scheduled in [Table 9-3](#).

The 49-item ARCI is a shortened version (49 true-false items) compiled by Martin et al. from the 550-item ARCI originally developed by Haertzen. This version contains 5 scales, which measure the following effects: Euphoria - MBG scale; Stimulant effects - Amphetamine (A) scale and Benzedrine Group (BG) scale; Dysphoria - LSD scale; and Sedation - PCAG scale. Subjects indicate their responses by selecting “False” or “True.” One point is given for each

response that agrees with the scoring direction on the scale (i.e., True items receive a score of 1 if the answer is “True;” no points are given when the answer is opposite to the scoring direction).

The following scales will be administered:

- *Euphoria*: Morphine-Benzedrine Group (MBG) scale
- *Stimulant effects*: Amphetamine (A) scale, Benzedrine Group (BG) scale
- *Dysphoria*: Lysergic Acid Diethylamide (LSD) scale
- *Sedation*: Pentobarbital-Chlorpromazine-Alcohol Group (PCAG) scale

The items pertaining to the ARCI scales are presented in [Table 9-7](#).

**Table 9-7. ARCI Scales Descriptions**

Question	Scale				
	A	PCAG	MBG	BG	LSD
My speech is slurred		T			
I am not as active as usual		T			
I have a feeling of just dragging along rather than coasting		T			
I feel sluggish		T			
My head feels heavy		T			
I feel like avoiding people, although I usually do not feel this way		T			
I feel dizzy		T			
It seems harder than usual to move around		T			
I am moody		T			
People might say that I am a little dull today		T		F	
I feel drowsy		T			F
I am full of energy		F			
Today I say things in the easiest possible way			T		
Things around me seem more pleasing than usual			T		
I have a pleasant feeling in my stomach			T		
I feel I will lose the contentment that I have now			T		
I feel in complete harmony with the world and those about me			T		
I can completely appreciate what others are saying when I am in this mood			T		
I would be happy all the time if I felt as I feel now			T		
I feel so good that I know other people can tell it			T		
I feel as if something pleasant had just happened to me			T		
I would be happy all the time if I felt as I do now			T		F
I feel more clear headed than dreamy		F	T	T	
I feel as if I would be more popular with people today	T		T		

Question	Scale				
	A	PCAG	MBG	BG	LSD
I feel a very pleasant emptiness	T		T		
My thoughts come more easily than usual	T		T	T	
I feel less discouraged than usual	T		T		
I am in the mood to talk about the feelings I have			T	T	
I feel more excited than dreamy	T	F			
Answering these questions is very easy today a	T			T	
My memory seems sharper to me than usual	T			T	
I feel as if I could do these tests for hours a	T			T	
I feel very patient	T				F
Some parts of my body are tingling	T			T	T
I have a weird feeling	T				T
My movements seem faster than usual				T	
I have better control over myself than usual				T	
My movements seem slower than usual				F	
I find it hard to keep my mind on a task or job				F	
I don't feel like reading anything right now				F	
It seems I'm spending longer than I should on each of these questions					T
My hand feels clumsy					T
I notice my hand shakes when I do these tests a					T
I have a disturbance in my stomach					T
I feel an increasing awareness of bodily sensations					T
I feel anxious and upset					T
I have unusual weakness of my muscles					T
A thrill has gone through me one or more times since I started this test		F			T
My movements are free, relaxed, and pleasurable					F

Abbreviations: A = Amphetamine; ARCI = Addiction Research Center Inventory; BG = Benzedrine Group; LSD = Lysergic acid diethylamide; MBG = Morphine-Benedrine Group; PCAG = Pentobarbital-Chlorpromazine-Alcohol Group.

T = True item

F = False item

a. Question modified slightly for computerized presentation.

Responses to individual items will be included. If one of the individual items is missing, the associated scale(s) score will not be calculated.

### 9.3 Analysis of Pharmacodynamics Measures

The primary PD endpoint of this study is the maximum (peak) effect (Emax) over 24 hours for Drug Liking (“at this moment”), assessed on a bipolar (0 to 100 points) visual analog scale (VAS). This endpoint will be summarized with descriptive statistics. Placebo will be pooled across all cohorts.

$E_{max}$  as well as  $T_{max}$  and TA\_AUE of key secondary PD endpoints, Overall Drug Liking, Take Drug Again, and High VAS will be summarized similarly by treatment for the Completer population using descriptive statistics. All PD measures at each time point will be summarized by treatment using descriptive statistics and presented graphically. Derived endpoints will be summarized by treatment and paired difference using descriptive statistics.

A mixed-effects model will be used to compare PD endpoints between Kratom dose levels and placebo for all primary and secondary PD endpoints other than the 12-hour postdose results from Drug Similarity VAS and  $TE_{max}$  and  $TE_{min}$  endpoints. The model will include dose level as a fixed effect and the baseline score as a covariate [where applicable]. P-values for key components of variance, least-square means (LSmeans), and 95% CI for contrasts will be output for each pairwise comparison for Kratom dose levels versus placebo.

For each PD endpoint, the following comparison will be made:

- Kratom 1 g vs. Placebo
- Kratom 2 g vs. Placebo
- Kratom 4 g vs. Placebo
- Kratom 6 g vs. Placebo
- Kratom 8 g vs. Placebo

The Hodges-Lehmann estimate of the location shift, the asymptotic confidence limits, and the asymptotic standard error estimate will be used to estimate the 95% CIs of  $TE_{max}$  and  $TE_{min}$  secondary endpoints between the Kratom dose levels and placebo. The asymptotic standard error estimate is based on the length of the CIs. Rank sums and p-values from the Wilcoxon Rank Sum test will also be output.

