**Table 9-1. Pupillometry Schedule**

Pupillometry - Scheduled Time Points
Day 1: predose and 0.5, 1, 1.5, 2, 2.5, 3, 4, 6, 8, 10, and 12 hours postdose
Day 2: 24 hours postdose

Windows for timed pupillometry measurements are presented in [Table 9-2](#).

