**Table 9-2. Acceptable Windows for Timed Pupillometry Measurements**

Elapsed Time	Accepted Window
Predose (Day 1)	Within 60 minutes prior to study drug administration
Postdose	Within 5 minutes following collection of PK blood sample

The following Pupillometry endpoints will be derived.

- Maximum pupil constriction as assessed by the difference between initial pupil diameter and minimum pupil diameter (MPC)
- Time to maximum pupil constriction
- Pupillometry area over the curve (time-averaged pupillometry area over the effect curve relative to baseline [TA\_PAOC]). TA\_PAOC will be calculated as the area over the effect curve relative to baseline divided by the time from time 0 to the last time point post-dose or specific time point.

Pupil diameter will be summarized by treatment, visit and time point using descriptive statistics. Derived endpoints will also be summarized by treatment using descriptive statistics.

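### Do the 'paired difference' and 'components of variance' outputs, and the lack of sensitivity analyses, leave the pharmacodynamic analysis undefined?

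*SAP*

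**What the plan says.** SAP 9.3 pools the control group ("Placebo will be pooled across all cohorts") and lists five comparisons: 1, 2, 4, 6 and 8 g, each against placebo. On the model it says "The model will include dose level as a fixed effect and the baseline score as a covariate", the covariate applying only where there is one. On output it says "P-values for key components of variance, least-square means (LSmeans), and 95% CI for contrasts will be output", and adds that this is done "for each pairwise comparison for Kratom dose levels versus placebo". No random term, covariance structure or degrees-of-freedom method is named.

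For descriptive output, SAP 9.3 says "Derived endpoints will be summarized by treatment and paired difference using descriptive statistics". SAP 9, protocol 8.5 and the protocol synopsis say the same. SAP 9.1 omits the paired element for pupillometry: "Derived endpoints will also be summarized by treatment using descriptive statistics".

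On design, SAP 3.1 and Table 3-1 put each subject in one cohort with one single oral administration, and SAP 3.4 randomises 6:2 within each cohort. SAP Table 9-3 and SAP 9.2.1 show no predose score for Drug Liking, Overall Drug Liking or Take Drug Again. High VAS has one, as does pupillometry ("Day 1: predose and 0.5, 1, 1.5, 2, 2.5, 3, 4, 6, 8, 10, and 12 hours postdose"). Hodges-Lehmann and Wilcoxon methods are planned for the times of maximum and minimum effect only.

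**The concern.** Three things look wrong on a first reading.

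1. A paired difference needs a pair. No subject receives both kratom and placebo, so there is no between-treatment pair. A pre-post pair needs a predose score, and Drug Liking (the primary PD endpoint), Overall Drug Liking and Take Drug Again have none. For three of the four leading PD endpoints the promised summary cannot be produced under either paired reading.
2. A mixed-effects model needs a random effect. With one derived value per subject, a subject effect cannot be separated from residual error, so a p-value for a variance component has no literal content.
3. The 95% CIs assume equal variances across groups and, because placebo is pooled without a cohort term, no cohort effect. Neither assumption has a planned sensitivity analysis.

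These contrasts are the only planned inferential comparison for peak effect, and protocol 1.3 says that the trial, PD effects included, is to help set the dose range of a future abuse potential study. If the output were truly undefined, or the intervals badly calibrated with a better method at hand, the plan should say more.

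**Working it through.** **Inputs.** Five cohorts of 8 at 6:2 (SAP 3.1, 3.4) give 30 kratom subjects (6 per dose) and 10 placebo subjects. The documents give no SD, intraclass correlation (ICC) or share of neutral scores, and no sample size was calculated (SAP 3.5). Every coverage figure below is therefore conditional on assumed values.

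**Can the main output be produced?** For an endpoint without a predose score there are 40 values and 6 group means:

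- residual df = 40 − 6 = 34 (33 with a baseline covariate);
- 95% half-width for dose versus pooled placebo = t(0.975, 34) × SD × √(1/6 + 1/10) = 2.032 × 0.516 × SD = 1.05 SD.

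The subject and residual variance matrices are both the identity, so their joint rank is 1 and the only variance parameter is the residual. Fitted in PROC MIXED with dose and baseline alone, the model gives the ordinary least-squares estimates, the same residual variance and the same CIs as ANOVA or ANCOVA. Nothing numerical turns on the label.

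**How does the SAP use its own terms?** SAP 8.5.2 defines the PK power model with an intercept, a slope on ln(dose) and an error term, then calls it a mixed-effect model run in PROC MIXED. So the SAP uses that label for a model with no random term. PROC MIXED prints F-tests for dose and baseline, which is the natural content of the variance p-values. For the paired wording, SAP 9.3 uses 'pairwise' for the dose-versus-placebo contrasts a few lines later.

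**Unequal variances** (normal data, 100,000 trials per set, coverage of the nominal 95% CI):

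| Assumed SDs, lowest to highest dose | Common variance, lowest dose | Common variance, highest dose |
|---|---|---|
| equal | 95.0% | 95.1% |
| 0.8 to 1.2, placebo 0.8 | 98.0% | 92.3% |
| 0.7 to 1.4, placebo 0.5 | 99.4% | 89.2% |
| 5 to 18, placebo 3 | about 100% | 86.0% |
| 3 to 15, placebo 2 | about 100% | 83.6% |

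Welch intervals hold 94.7% to 95.1% in all these sets. Peak Drug Liking, however, is bounded and likely to collect at the neutral score of 50. With many scores exactly neutral (up to 90% on placebo), Welch drops to 85.2% at the lowest dose while the common-variance CI covers 99.9%. With a ceiling at high doses, the highest-dose figures are 99.9% to 100% for common variance and 86.2% to 87.5% for Welch. If 80% or 90% of placebo scores are neutral, all ten are identical in 0.8^10 = 11% or 0.9^10 = 35% of trials, and Welch then has no placebo variance to use.

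**Omitted cohort effect.** Let the total variance be 1, with cohort variance τ² = ICC and residual variance σ² = 1 − ICC.

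- True variance of dose minus pooled placebo = 0.8τ² + (4/15)σ².
- Expected value of the variance the model uses = (4/15)(σ² + 8τ²/34).
- At ICC 0.10 these are 0.320 and 0.246. The effective critical value is 2.032 × √(0.246/0.320) = 1.78, which on 34 df is about 91.6% coverage.

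Simulation gives 93.5%, 91.6% and 87.9% at ICC 0.05, 0.10 and 0.20. The two repairs compare as follows:

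- Cohort as a random effect with 34 df: 93.9%, 93.0% and 91.8%. The cohort variance rests on five placebo pairs and is estimated as zero in about 53%, 48% and 38% of trials. CIs are 8% to 13% wider.
- Cohort as a fixed effect: coverage is 95.0%, but each dose is then compared only with the two placebo subjects in its own cohort. The half-width is t(0.975, 30) × √(1/6 + 1/2) = 2.042 × 0.816 = 1.67 residual SDs. At ICC 0, against 1.05, that is about 59% wider.

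**The case for a change.** The strongest case for a change is that the paired phrase stands in four places across both documents, so it is hard to call a single typing error. SAP 9.1 leaves it out for pupillometry, and SAP 13 records no departure from the protocol. The authors could be exact when they chose: SAP 8.5.2 gives an equation, a procedure and a fallback. SAP 5 treats analyses done after database lock or unblinding as post hoc, so an ambiguity should be settled beforehand. Clearer words in the SAP would cost almost nothing.

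It stands that the phrase is wrong for this design and that the model label is loose. It does not follow that the analysis is open. Only one descriptive item is unclear, and any sensible reading of it largely repeats the planned contrasts. SAP 14 places table layouts in a separate document, where such row-level detail would normally sit. Rewording the protocol would also not be free, since protocol 12.2 sends amendments to the ethics board.

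On sensitivity analyses, coverage below 90% at the highest dose is possible under steep variance patterns. But those patterns are assumed, the direction reverses under others, and no single alternative is better throughout. Better degrees of freedom help the random-cohort model (94.7%, 94.1% and 93.2% with Satterthwaite at the same three ICCs) but do not remove the shortfall.

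**Conclusion.** No change to the plan follows. The paired and variance-component wording is a clerical slip that an analyst will resolve sensibly: differences of each dose from pooled placebo, and F-tests for dose level and baseline. Correcting it would alter no estimate, interval or conclusion; the dose-versus-placebo half-width stays at 1.05 SD on 34 df either way.

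The missing sensitivity analyses are a fair trade-off. Highest-dose coverage of the planned CI ranges from 83.6% to 95.1% in the normal scenarios, but Welch falls to 85.2% on bounded data, a random cohort term is a partial repair, and a fixed cohort term costs intervals more than half as wide again. All of this rests on assumed SDs, neutral shares and ICCs, and the variance and cohort effects must not be added together.

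The consequence is also small. The primary safety result is untouched, PD is secondary, protocol 3.2 calls the trial's approach hypothesis-forming, escalation uses blinded review (protocol 3.2, SAP 12), and no decision rule uses these intervals. Confidence is high on the wording, which can be read directly. It is lower on how far the assumptions would fail in practice, which the documents do not allow anyone to judge.

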## 10 SAFETY ANALYSIS

Safety assessments will include AEs monitoring, laboratory tests, vital signs (blood pressure, pulse, respiratory rate, oxygen saturation, and body temperature), ECG assessments, physical examination findings, and C-SSRS.

Unless otherwise specified, all available data will be listed and summary tables for safety assessments will be presented for the safety population.

### 10.1 Adverse Events

An AE is defined as any untoward medical occurrence in a subject administered an investigational product and which does not necessarily have a causal relationship with the treatment. An AE can therefore be any unfavorable and unintended sign (including a clinically significant abnormal clinical laboratory finding, for example), symptom, or disease temporally

associated with the use of an investigational product, whether or not related to the investigational product.

Treatment-emergent AEs (TEAEs) are AEs not present prior to but reported following the exposure to study treatment or AEs already present that worsen in intensity or frequency following exposure to study treatment. All TEAEs will be assigned to the last treatment taken by the subject where the date and time of the last treatment dosing is on or before of the start date and time of the event. Any TEAE started during the follow-up period will be assigned to the last treatment that the subject has taken.

In case that the time of onset or time of resolution is unknown, treatment-emergent or assignment would be determined considering the worst case scenario and/or on case-by-case basis, as deemed appropriate. Treatment-emergent AEs with missing severity or relationship to study treatment will also be classified to the worst case (e.g., severe and/or related, as appropriate) in corresponding summaries.

An overall summary of AEs will be presented by treatment and overall including:

- Number of AEs reported, overall only
- Number of TEAEs reported
- Number (%) of subjects with at least one TEAE
- Number (%) of subjects with at least one study drug-related TEAEs (i.e., those with a relationship classified as ‘Reasonable Possibility’)
- Number (%) of TEAEs by relationship to study treatment (i.e., related or unrelated)
- Number (%) of TEAEs by toxicity grade
- Number of serious AEs (SAEs)
- Number (%) of subjects with at least one treatment-emergent SAE
- Number (%) of subjects with at least one study drug-related treatment-emergent SAE
- Number (%) of subjects with a TEAE leading to discontinuation
- Number (%) of subjects with outcome of death

Frequency tables will be presented by treatment and overall for the following:

- Number (%) of subjects with TEAEs by system organ class (SOC) and preferred term (PT)
- Number (%) of subjects with drug-related TEAEs by SOC and PT

Adverse events that led to discontinuation, SAEs, and adverse events with the outcome of death will be listed.

Severity assessment for AEs will be graded per the current CTCAE.

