 - Bowdle VAS Internal and External Perceptions composite scores (E_{max})
 - Drug Similarity VAS 12-hour postdose scores
- Pupillometry
 - Maximum pupil constriction as assessed by the difference between initial pupil diameter and minimum pupil diameter (MPC)

	
 ○ Time to maximum pupil constriction ○ Pupillometry area over the curve (time-averaged pupillometry area over the effect curve relative to baseline [TA_PAOC]) 																				
Investigational Product, Dose, and Mode of Administration:	
Kratom 500 mg capsules Manufacturer: Sun Distribution, Super Organics Mode of administration: Oral
																				
Placebo and Mode of Administration:	
Placebo-to-match kratom 500 mg capsules Mode of administration: Oral
																				
Study Population:	Healthy, male and female nondependent, recreational polydrug users with opioid experience																				
Planned Number of Subjects:	A total of 40 subjects (8 subjects in each of the 5 cohorts) will be included.																				

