3.3. Maximum Tolerated Dose

The Maximum Tolerated Dose (MTD) definition: Transient, mild or moderate AEs occurring at a given dose level will be evaluated by the SRC prior to dose escalation. If such AEs occurred in ≥ 3 subjects at a given dose level, dose escalation may be ceased and this dose level or the next lower one will be considered the MTD, or an intermediate dose level can be investigated. If such AEs occurred in ≤ 2 subjects depending on the particular adverse effects observed, the current dose level may be considered the MTD, or dose escalation may proceed.

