4.3.2.1.2. Cohort Stopping Rules

If any of the following safety concerns are observed, dosing of all subjects at the given dose level or higher will be suspended/halted and all available data will be evaluated by the SRC. Dose continuation (remaining subjects within a cohort or remaining dosing for a subject) or escalation should not proceed for any of, but not limited to, the following reasons:

- If 1 kratom-related SAE occurs in a cohort
- Moderate or severe AEs in 50% of the subjects in the cohort or more

Dose escalation will be discussed during the SRC meeting and may be stopped depending on Principal Investigator's or Sponsor's decision.

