#### **3.4 Randomization and Unblinding Procedures**

In each cohort, subjects will be randomized 6:2 (active: placebo). The clinical site will generate the randomization code with a computer program according to the study design, the number of subjects and the number of treatments. Once generated, the randomization code will be final and will not be modified.

The randomization code will not be available to the personnel of the bioanalytical facility until the bioanalytical phase of the study has been completed. The treatment assignment (active or placebo) will not be known by the study participants. Study participants will be informed of the dose range they could receive but will not be informed of the actual dose assigned to them.

Furthermore, the randomization code will not be available to the Investigator and clinical staff involved in the collection, monitoring, revision, or evaluation of AEs, as well as clinical staff who could have an impact on the outcome of the study including the pharmacokineticist (or

delegate) and biostatistician, until all the CRFs have been approved and signed and the bioanalytical phase of the study has been completed.

The preparation and/or administration of the products will be done by designated personnel who are not directly involved in the clinical aspects of the trial.

The randomization code must not be broken except in emergency situations where the identification of a subject's study treatment is required by an Investigator for further treatment to the subject or to complete a SAE report. Randomization information will be held by designated individual(s). The date and reason for breaking the blind must be recorded.

The results of the PD analyses will be made available only to the personnel responsible for evaluating the safety data before proceeding with the next dose level.

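### SAP 10.1 tabulates AE severity by event only, so no summary it lists gives the number of subjects per dose with a moderate or severe TEAE

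*SAP*

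**What the plan says.** SAP 10.1 plans an overall AE summary by treatment. Severity enters through one row: "Number (%) of TEAEs by toxicity grade". Neighbouring rows are explicitly in subjects, for example "Number (%) of subjects with at least one TEAE". The other subject rows cover drug-related TEAEs, treatment-emergent SAEs (any and drug-related), TEAEs leading to discontinuation, and death. The two SOC/PT frequency tables also count subjects, without grade. The relationship-to-treatment row counts events too, but it has a subject-level companion; the severity row has none.

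SAP 5.1 sets the columns as active dose levels and pooled placebo. SAP 10 says available safety data will be listed.

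The protocol's dose rules count subjects. Protocol 4.3.2.1.2 names as a reason to halt: "Moderate or severe AEs in 50% of the subjects in the cohort or more". Protocol 3.3 starts from this statement: "Transient, mild or moderate AEs occurring at a given dose level will be evaluated by the SRC prior to dose escalation". It then sets its threshold with "If such AEs occurred in ≥ 3 subjects at a given dose level". Under Protocol 3.2 the Safety Review Committee (SRC) reviews the data blinded, during the study.

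Severity is graded by CTCAE (Protocol 7.2, SAP 10.1), while both rules use the words mild, moderate and severe. Neither document states how one scale maps to the other.

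**The concern.** In a dose-escalation study the basic tolerability result is how many people at each dose had an event of a given severity. SAP 10.1 gives how many events had each grade. With six kratom subjects per dose, one person reporting several events can dominate such a row, and the row does not show that this has happened.

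The SAP does not state the denominator of the event percentage. SAP 5.1 bases percentages on available data, so I assume it is the total number of TEAEs in the column. That total differs from dose to dose, and many mild events at one dose will lower the share that is moderate or severe.

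At stake is how clearly the final report describes tolerability by dose. Protocol 1.3 says the results are to help choose the dose range for a later human abuse potential study.

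**Working it through.** **Inputs.** Protocol synopsis: "A total of 40 subjects (8 subjects in each of the 5 cohorts) will be included". Allocation is 6:2 in each cohort. So 5 × (6 + 2) = 40, with 5 × 6 = 30 on kratom and 5 × 2 = 10 on placebo. The AE columns are therefore 6 subjects per dose and 10 for pooled placebo. The documents give no power or precision figure on this point to reproduce. All event patterns below are assumptions, used only to show what the planned cells can and cannot separate.

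**Step 1: what the event count says about subjects.** Let *a* be the subjects with any TEAE and *k* the moderate-or-worse events (*k* ≥ 1). The number of affected subjects can lie anywhere from 1 to min(*k*, *a*), if there are enough mild events to account for the other subjects. With *a* = 5: *k* = 4 allows 1 to 4 affected subjects, and *k* ≥ 5 allows 1 to 5.

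**Step 2: identical cells, different tolerability.** Entries are (mild, moderate) events for each of six subjects.

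- Dose C: (1,4), (1,0), (1,0), (1,0), (1,0), (0,0)
- Dose D: (1,1), (1,1), (1,1), (1,1), (1,0), (0,0)

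| Cell | Dose C | Dose D |
|---|---|---|
| Subjects with any TEAE (planned) | 5/6 | 5/6 |
| TEAEs (planned) | 9 | 9 |
| Moderate TEAEs (planned) | 4 (4/9 = 44.4%) | 4 (4/9 = 44.4%) |
| Subjects with a moderate TEAE (not listed) | 1/6 = 16.7% | 4/6 = 66.7% |

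**Step 3: the cohort rule.** For a full cohort the threshold is 0.5 × 8 = 4 subjects. Dose D reaches it on kratom subjects alone, 4/8 = 50%. Dose C cannot: even if both placebo subjects in its cohort were affected, the count is 1 + 2 = 3, and 3/8 = 37.5%. The same planned cells therefore fall on both sides of the rule. Because placebo is pooled across cohorts, a row by dose level (6 subjects) would not rebuild the 8-subject count either.

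**Step 4: the order can reverse.** Dose A has (0,5), (1,0), (1,0), (1,0), (1,0), (0,0). Dose B has the pattern of dose D. Both show 5/6 subjects with a TEAE and 9 TEAEs. By event, A looks worse: 5/9 = 55.6% against 4/9 = 44.4%. By subject, B is worse: 4/6 against 1/6.

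**Step 5: how often.** Simulation of pairs of 6-subject doses, 100,000 pairs per setting. Assumptions: the stated risk per subject of a moderate-or-worse event; mild events Poisson with mean 6 per group; and 1 moderate-or-worse event per affected subject, or a geometric number with mean 2 or 3. Among pairs whose observed subject counts differ, the share ranked the opposite way was:

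| Subject risks | Events per affected subject | By event count | By % of events |
|---|---|---|---|
| 0.2 v 0.5 | 1 / mean 2 / mean 3 | 0% / 5.6% / 8.1% | 7.0% / 10.9% / 12.6% |
| 0.3 v 0.5 | 1 / mean 2 / mean 3 | 0% / 8.7% / 11.7% | 11.0% / 15.8% / 17.1% |
| 0.2 v 0.4 | 1 / mean 2 / mean 3 | 0% / 5.9% / 8.3% | 7.2% / 11.4% / 12.4% |

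Reversal is a minority outcome: 7% to 17% by percentage and 0% to 12% by count.

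**Step 6: the MTD count.** Protocol 3.3 counts subjects with transient mild or moderate AEs. Every such kratom subject is also in the any-TEAE row, so that row is an upper bound. A dose with fewer than 3 subjects there has not reached the threshold. If no event is severe, the two counts differ only through the condition that the AE be transient.

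**The case against.** The case on the other side has five parts.

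- **Other subject-level rows exist.** A reader might infer that the planned tables cannot show which doses were tolerated. The documents do not support that: subject rows for SAEs, discontinuation, death and any TEAE are direct tolerability measures.
- **The MTD does not hang on this row.** A reader might also infer that the tables leave the MTD impossible to check. Step 6 shows that the any-TEAE row bounds the count. Protocol 3.3 is also discretionary, so no table alone could settle it. The clear gap is the moderate-or-severe count.
- **The rules are applied during the study.** The SRC does this on blinded data, not from the final tables, so no escalation or stopping decision depends on SAP 10.1. This stands in full.
- **Listings allow a hand count.** With six kratom subjects per dose that is easy, so the information is untabulated, not lost. But a primary tolerability result should not depend on each reader's own count. Under SAP 5, an analysis performed after database lock or unblinding is labelled post hoc and exploratory, so a table added late would lose its pre-specified standing.
- **The shells are not available.** SAP 14 places table layouts in a separate document, and the list in 10.1 may not be exhaustive. The claim is therefore limited to the summaries that the SAP lists.

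The event row also prints a count beside its percentage, so a reader is not left with the percentage alone. That helps in many cases, but not in steps 2 to 4, where the counts are equal or themselves reversed.

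**Conclusion.** The point holds as a reporting gap that should be closed. SAP 10.1 gives severity by event only, and no summary it lists gives subjects per dose with a moderate or severe TEAE, although that is the unit of the cohort rule and the natural unit for the primary objective. Identical planned cells can hide 1/6 against 4/6 affected subjects. That result is arithmetic on assumed patterns and shows what is possible, not what is likely. The 7% to 17% reversal figure rests on the simulation's assumed risks and event rates and on total TEAEs as the denominator. It does not support a claim that the table will usually rank doses wrongly. The consequence is confined to the clarity of the final report.

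**What to change.** In SAP 10.1, add (or substitute for the event row) the number and percentage of subjects by worst TEAE toxicity grade. Give it for all TEAEs and for drug-related TEAEs, by dose level (denominator: kratom subjects dosed) and pooled placebo.

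Add one row by cohort, including that cohort's placebo subjects, for subjects with a moderate or severe AE, since Protocol 4.3.2.1.2 uses the cohort as its denominator.

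State how CTCAE grades map to mild, moderate and severe, so that the rows and the protocol rules use the same terms.

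In the step 2 example the first row would read 1/6 (16.7%) for dose C and 4/6 (66.7%) for dose D. The data are already collected and no clinical rule changes. The cost is a short SAP edit and one or two extra rows or table shells, made before database lock and unblinding.
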